### **5.0 Number of Subjects**

The proposed single-site study will be conducted at The Ocular Surface Institute at the University of Houston College of Optometry. Up to 60 subjects will be screened for study inclusion, with the goal of completing 20 subjects. Subjects that screen fail may be rescreened for study inclusion up to 3 additional times at the discretion of the study investigator.

Currently, there is no information on the time from contact lens fitting to the development of LWE. This pilot study is designed to collect data which can be used to determine the sample size required to conduct a larger-scale clinical trial. It is anticipated that enrolling 20 subjects will approach the requirements of the central limit theorem for statistical analysis. Since the subjects in the study will be wearing FDA-approved contact lenses on a daily wear modality (i.e. not sleeping in contact lenses), the study does not present more than minimal risk to the subject and a power analysis is not required.

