## **7.0 Study Endpoints**

The primary study endpoints are as follows:

- Examine the development of LWE post-contact lens fitting at the following time points
  - 1-week post contact lens fitting
  - 2 hours after contact lens fitting

The secondary study endpoints are as follows:

- Examine the level of expression in ocular surface tear MMPs post-contact lens fitting at the following time points
  - Pre-contact lens fitting
  - 1-week post contact lens fitting
  - 2 hours after contact lens fit

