## FULL PROTOCOL TITLE: The Impact of Contact Lens Coefficient of Friction (CoF) on the Development of Lid Wiper Epitheliopathy (LWE)

Korb LWE Grading				
Grading	Description	Height (%)	Width (mm)	Final score (grade)
0	no LWE	<25	<2	<0.25
1	mild LWE	25-50	2-4	0.25-1.00
2	moderate LWE	50-75	5-9	1.25-2.00
3	severe LWE	>75	>10	2.25-3.00

\*Final LWE score is the average of the LWE Height and Width

The tears collected by capillary tubes will be stored at -80°C until luminex multibead analysis. 15 µg of total protein will be analyzed for matrix metalloproteinases (MMP)-1, -2, -7, -9, -10. Pre- and post-contact lens wear concentrations of MMP will be compared for each subject. MMPs are a family of zinc proteases and an increase in MMP expression occurs in response to a wide range of stimuli, including adhesion molecules, growth factors, cytokines and hormones and is associated with ocular surface damage. The correlation coefficient, r, will be determined between LWE and the tear film levels of MMPs.

A  $p \leq 0.05$  will be considered statistically significant.

Layman's Description of Procedures	
Patient demographics	The subjects will be asked questions about their age, sex, race and ethnicity.
History	The subjects will be asked questions about their systemic health, ocular disease and surgical history.
Concomitant Medications	The subjects will be asked questions about their current ocular and systemic medications.
Habitual Contact Lens Information	The subjects will be asked questions about how they use their current contact lenses, such as their current contact lens brand and wear time, as performed during a normal eye exam.
Auto-refraction	A machine will shine light into a subject's eye and will estimate their prescription using different powered lenses without making contact with the eye.
Oculus Keratograph	A machine uses a video camera to determine how long it takes for a subject's tear film to

**FULL PROTOCOL TITLE: The Impact of Contact Lens Coefficient of Friction (CoF) on the Development of Lid Wiper Epitheliopathy (LWE)**

	evaporate and the height of the pooled tears between the lower lid and the ocular surface without making contact with the eye.

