## **FULL PROTOCOL TITLE: The Impact of Contact Lens Coefficient of Friction (CoF) on the Development of Lid Wiper Epitheliopathy (LWE)**

### Addendum: Statistical Analyses

Statistical analyses were performed in SPSS v26 (IBM) and GraphPad. When data were not significantly different from a normal distribution (non-invasive tear break up time, tear meniscus height), statistical analyses were conducted using paired t-tests and repeated-measures analyses of variance (RM-ANOVA), with adjusted post-hoc t-tests, when appropriate. For NITBUT and TMH, the RM-ANOVA included two repeated factors—lens type (Acuvue Oasys and Air Optix Night and Day) and time (baseline, 2 hours post-fitting and 7 days after lens fitting). For data that was not normally distributed (LWE staining), Friedman and Mann-Whitney non-parametric statistics were performed. MMP concentrations were adjusted by multiplying raw values by the dilution factor. Tear film MMP concentrations under the level of detection (LOD) were divided by  $\sqrt{2}$  (Croghan et al. 2003). Outliers in MMP data sets were analyzed using the ROUT function in Graphpad Prism 8.4.1 and were removed prior to analysis.

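### MMP values are deleted on a ROUT flag alone, with no documented assay or sample fault required and no analysis that keeps all values

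*Combined protocol and SAP*

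**What the plan says.** Section 7.0 (Study Endpoints) names one secondary endpoint: "Examine the level of expression in ocular surface tear MMPs post-contact lens fitting at the following time points". The time points are before fitting, 2 hours after and 1 week after.

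Section 8.0 (Procedures Involved), in the text below the LWE grading table, lists five analytes (MMP-1, -2, -7, -9 and -10). It states: "Pre- and post-contact lens wear concentrations of MMP will be compared for each subject". As background it says that "an increase in MMP expression occurs in response to a wide range of stimuli" and that this "is associated with ocular surface damage". The significance level is 0.05.

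The Addendum: Statistical Analyses gives the outlier rule: "Outliers in MMP data sets were analyzed using the ROUT function in Graphpad Prism 8.4.1 and were removed prior to analysis". It does not give:

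- the ROUT setting Q;
- whether ROUT was run on raw or log values;
- what one data set is (analyte, lens, visit, or a pool of these);
- how many values were removed;
- what happens to a within-subject pair when one of its values is deleted;
- which test was used for MMP.

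**The concern.** ROUT identifies values that are unusual relative to a roughly normal scatter. It does not show that a value is an error. If concentrations are right-skewed and ROUT is run on the raw scale, the values it flags are almost all genuine high readings. Section 8.0 associates high MMP with ocular surface damage, so these readings are likely to carry the information the endpoint was chosen for. The rule deletes them without asking whether anything went wrong with the sample or the assay, and no result with them kept is available for comparison. At stake are the false-positive rate and the estimated size of a change in the MMP comparison.

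**Working it through.** **Reading the text.** MMP and the tear samples are dealt with in Section 7.0, Section 8.0, Section 21.0 (Specimen Use and Banking) and the addendum. None gives an assay-rejection or sample-fault criterion, or an analysis with all values kept. The ROUT flag is therefore the only stated condition for removal.

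**Inputs from the documents.** 20 completers (Section 5.0), three time points (Section 7.0), two lenses worn one per eye (Section 1.0), five analytes and a 0.05 level (Section 8.0). The unit of application could be 5 × 2 × 3 = 30 columns of 20 values, 5 × 2 = 10 columns of 60 (visits pooled), or 5 columns of 120 (lenses pooled too). The plan gives no MMP figure to reproduce.

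**Assumed inputs (none from the documents).** Log-normal MMP with log-SD 0.5, 0.8 or 1.0; within-subject log correlation 0.5; raw-scale ROUT at Q = 1%; one lens; pre-fitting compared with 2 hours; any rise applied to both post visits.

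**ROUT approximation.**

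- Centre: weighted mean with weights 1/(1 + (r/s)²), where r is the absolute residual.
- Scale: s = 68.27th percentile of r × n/(n − 1).
- Test: two-sided p from r/s on a t distribution. Working outward through the largest 30% of residuals, stop at the first value with p < Q × (number of values at least that extreme)/n, and remove it and all beyond it. With n = 20, a lone extreme value needs p < 0.01 × 1/20 = 0.0005.

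**Results** (10,000 simulated data sets per setting; 4,000 for signed-rank and Friedman; 2,000 for Mann-Whitney):

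| Quantity | log-SD 0.5 | 0.8 | 1.0 |
|---|---|---|---|
| Valid values removed, per visit | 1.9% | 5.1% | 7.5% |
| Valid values removed, visits pooled | 2.1% | 6.0% | 9.1% |
| No true effect, Friedman, per visit | 6.0% | 7.3% | 7.8% |
| No true effect, signed-rank, per visit | 6.7% | 8.5% | 9.5% |
| No true effect, paired t, per visit | 7.0% | 9.3% | 10.8% |
| No true effect, Mann-Whitney (ignores pairing), per visit | 2.1% | 4.2% | 6.0% |
| No true effect, paired t, visits pooled | 5.2% | 4.7% | 4.7% |
| No true effect, paired t, all values kept | 4.8% | 3.9% | 3.3% |
| Uniform 1.5-fold rise, all values | 1.51 | 1.54 | 1.57 |
| Same, per visit | 1.52 | 1.54 | 1.57 |
| Same, visits pooled | 1.47 | 1.41 | 1.38 |
| 4 of 20 rise 4-fold, all values | 1.61 | 1.64 | 1.68 |
| Same, per visit | 1.20 | 1.30 | 1.34 |
| Same, visits pooled | 1.11 | 1.16 | 1.18 |

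The rise rows are average ratios of means. Over 99.9% of removed values lie above the median. Per visit, 1.9% and 7.5% of 20 are 0.38 and 1.5 values. Simulation error on a 5% rate is √(0.05 × 0.95/10,000) = 0.2 points, or 0.5 points at 2,000. A hand check on the responder case: (16 × 1 + 4 × 4)/20 = 1.6.

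**Why the unit matters.** Per visit, a uniform 1.5-fold rise multiplies the centre and the scale alike, so the same values are flagged and the ratio survives. With visits pooled, the cut-off is common and more post than pre values are removed: 3.2 / 8.1 / 11.4% against 0.4 / 2.8 / 5.2%. That shrinks the rise. Power of a log-scale paired t then goes from 93 to 91, 57 to 49 and 41 to 32%, while raw-scale paired-t power is about unchanged. A likely reason for the per-visit false positives is that each visit gets its own cut-off from its own chance spread, so upper tails are cut unequally and the test ignores this.

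**Robustness.** Separately coded versions of the approximation gave 0.35 and 1.52 of 20 values removed at log-SD 0.5 and 1.0, per-visit paired-t rates of 7.3 to 7.7% and 10.7 to 12.2% at the same two spreads, and a pooled ratio of 1.44 / 1.35 / 1.31 for the uniform rise. Varying the correlation from 0 to 0.8 moves the per-visit paired-t rate from 9.5 to 5.7% (log-SD 0.5) and from 17.3 to 8.0% (1.0). Varying Q from 0.1% to 10% moves it from 5.4 to 7.7% and from 8.8 to 12.2%. Pooled stays at 4.0 to 5.6% throughout. With ROUT on log values, or on normal data, at most about 0.1% of values are removed.

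**The case against.** ROUT is a named, reproducible rule. MMP is a secondary endpoint in a pilot without a power analysis. Every quantity that drives the illustration is assumed. The responder scenario was chosen, and the two-lens contrast was not simulated. All of this stands, and it limits the severity. It does not supply a reason to delete a valid reading, and with about 20 subjects each deletion weighs more.

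The paired-t figures should not lead. The addendum names no MMP test; it keeps paired t for data not shown to depart from normality and uses Friedman and Mann-Whitney for the skewed LWE data. If that rule carried over, the closer figures are 6 to 8% and 2 to 6%.

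Preferring an all-values main analysis is partly judgement. Stating Q, scale, unit and counts beside an all-values sensitivity analysis would close the reporting gap, but the main result would still rest on deletion without cause.

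A reader might infer more from Section 5.0, which says "This pilot study is designed to collect data which can be used to determine the sample size required to conduct a larger-scale clinical trial": that a trimmed MMP spread would make the later trial too small. The documents do not support this. The preceding sentence there is about the time to development of LWE, and nothing says MMP spread will be used. Trimming can also shrink the raw difference along with the spread, so the spread alone would not settle the sample size.

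**Conclusion.** The point holds as a gap in how the secondary endpoint is analysed: removal rests on a statistical flag, with no fault criterion and no all-values result. It should be corrected; confidence in the size of the effect is moderate at best.

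On the assumed inputs, per-visit removal gives false-positive rates of about 6 to 8% (Friedman), 7 to 10% (signed-rank) or 7 to 11% (paired t), with Mann-Whitney at about 2 to 6%. Removal pooled over visits does not inflate false positives but shrinks a uniform 1.5-fold rise to roughly 1.3 to 1.47. Under either unit, a 4-fold rise in 4 of 20 subjects is largely trimmed away: from about 1.6–1.7 to 1.2–1.35 per visit, or 1.1–1.2 pooled. If ROUT was run on log values or the data are near normal, the effect is negligible. The documents do not show which case applies.

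Three stronger readings are not supported. The primary LWE comparison is not affected, because the rule is applied only to MMP. The documents do not show that the MMP results are wrong. And a rise is not a stated hypothesis: Section 7.0 speaks only of the level of expression, and the importance of high values is inferred from the background in Section 8.0.

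**What to change.** Re-run the MMP analysis with all valid values kept and make that the main result, either log-transformed and analysed within subject, or by a signed-rank test on paired differences. Exclude a value only for a documented assay or sample fault. Show the ROUT-trimmed result as a sensitivity analysis, stating Q, raw or log scale, the unit to which ROUT was applied, and the number of values removed by analyte, lens and visit. Name the MMP test in the addendum.

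The cost is revised wording and a re-run on existing data; no new samples are needed. The price is somewhat wider intervals, because extreme values stay in, and a log-scale result is read as a ratio, not as a difference in concentration.
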